1. PURPOSE OF THE STUDY AND BACKGROUND

1.1. Objective:

The objectives of this study proposal are:

Aim 1 (primary): Assess the feasibility, acceptability, and fidelity of the DIAL-SDM intervention, as measured in both nephrologist and patient coaching sessions by the Feasibility of the Intervention Measure,¹ Acceptability of the Intervention Measures,¹ and fidelity checklists for both nephrologist and patients' coaching sessions. We will also gather qualitative data from nephrologists, patient coaches, research coordinators, patients, and caregivers to guide the modification of the study protocol.

Aim 2: Generate preliminary effect sizes and examine the effect of the intervention on the following patient outcomes:

- (a) **Active patient participation in dialysis decision-making**, as measured by the Active Patient Participation Coding (APPC) scores from audio recordings of office visits.^{2,3}
- (b) **Shared dialysis decision-making**, as measured by the modified OPTION scale scores,⁴ from audio recordings of office visits, and the patient-reported Shared Decision-Making Questionnaire and the Decisional Engagement Scale.⁵
- (c) **Patients' initial choice of ESRD treatment options** (home vs. in-center dialysis vs. CM) at study entry and completion.
- (d) Patient report of **prognostic discussions**, as measured by the prognosis questionnaire.⁶
- (e) **Decisional conflict**, as measured by the decisional conflict scale.⁷
- (f) **Patient report of goal concordant care**, as measured by the goal concordant questionnaire.⁸

Aim 3: Aim 2: Generate preliminary effect sizes and examine the effect of the intervention on the following caregiver outcomes:

- (a) **Decisional conflict**, as measured by the decisional conflict scale.⁶
- (b) **Shared dialysis decision-making** as measured by the Shared Decision-Making Questionnaire and the Decisional Engagement Scale.^{4,5}

1.2. Background:

National guidelines recommend that nephrologists engage patients with chronic kidney disease (CKD) in shared decision-making (SDM) before initiating dialysis.^{9,10} More than 200,000 older adults receive dialysis for end-stage renal disease (ESRD),³ despite the high burden of treatment,¹¹⁻¹⁴ and guidelines encourage physicians to consider conservative management (CM), rather than dialysis, for older patients with poor prognosis.⁹ In older adults with multiple co-morbidities, dialysis may have minimal impact on survival but worsens quality of life (QoL) and entails frequent hospitalizations.^{17,18} They often prefer maintaining QoL over prolonging life.^{17,18} They wish to know prognostic information but nephrologists infrequently engage these patients in meaningful discussions about their preferences and prognosis, including CM.^{17,18} As a result, patients often overestimate prognosis and have unrealistic expectations for a cure.¹⁸⁻²³ Honest yet sensitive discussions about prognosis and treatment choices are associated with more realistic prognostic estimates and decisions better aligned with patients' preferences.^{24,25} However, changing decision-making conversations is not straightforward.^{26,27} There are currently no scientifically proven interventions to improve communication between nephrologists and older patients with CKD around shared decision-making (SDM) for dialysis initiation. Prior interventions with limited effectiveness that studied non-CKD patients generally addressed either clinicians' or patients' communication behaviors²⁸⁻³³ or used a third party to facilitate communication.^{34,35} Yet the **ecological framework** and prior studies of SDM suggest that attention to both clinician and patient communication behaviors is essential to facilitate difficult conversations in the emotionally-sensitive, value-driven, and highly personal context of serious illness such as CKD.³⁶⁻⁴² Therefore, **we need to improve the process of decision-making about the initiation of dialysis, enhancing patient-physician communications so that they can meaningfully share treatment decisions.** Patients' voices need to be heard when they are facing difficult choices that will determine the course and quality of their lives.

2. STUDY DESIGN

2.1. Overview

We propose a prospective, cluster-randomized clinical trial of **DIAL-SDM** vs Usual Care (UC) with nephrologists from the renal group at Strong Memorial Hospital, Highland Hospital, FF Thompson, and Rochester General Hospital as the unit of randomization and patients as the unit of analyses. Routine nephrology follow-up of patients in both arms will be at the discretion of nephrologists.

2.2. Rationale for Study Design

To examine the outcomes of the DIAL-SDM intervention for CKD patients ≥ 65 years (and their caregivers), a prospective, cluster-randomized design is preferred over a nonrandomized prospective design or retrospective design. If the results of this pilot study show feasibility and acceptability of the **DIAL-SDM** intervention (as hypothesized), we plan to design a larger-scale cluster randomized control trial.

3. CHARACTERISTICS OF THE RESEARCH POPULATION

3.1. Subject Characteristics

- (a) **Number of Subjects:** The study subjects include nephrologists, research coordinators, patient coaches, patients, and caregivers from Strong, Highland, FF Thompson, and Rochester General Hospital. The study will be performed between August 2021 and September 2025. Nephrologists (n= up to 16), in the Strong, Highland, FF Thompson, and Rochester General Renal Group will be eligible to participate and will provide informed consent. For physicians who withdraw from the study prior to the enrollment of their own participating patients, they will be replaced with additional physicians, therefore keeping the number of participating physicians up to 16. Research Coordinators (n=up to 3) who have assisted in the study will be eligible to participate in a qualitative interview and will provide informed consent. Patient Coaches (n=up to 3) who have assisted in the study will be eligible to participate in a qualitative interview and will provide informed consent. With a total sample size of 60 patients (approximately 5 patients per nephrologist depending on the total number of enrolled nephrologists), we would have 80% power at an alpha of 0.05, assuming a coefficient of variation of cluster sizes as high as 0.5 and an intraclass correlation coefficient of 0.1 to detect mean differences of at least 15 points (standard deviation 11) on the OPTION scale scores reflecting shared decision making between two groups. The data generated in this pilot study will be useful to generate effect size estimates for a future trial. We expect to enroll 36 caregivers assuming a 60% participation rate of caregivers. The proposed recruitment plan aligns with the goals of the K-23 which is a small pilot.
- (b) **Gender and Age of Subjects:** For patients, we will include men and women who are ≥65 years old. We expect the same distribution of men (48%) and women (52%) as of the general population. All adult caregivers (21-years or older) will be eligible to participate in the study. Based on prior research, we expect the following age distribution for caregivers: age 21-44 yrs. = 15%; 45-54 yrs. = 25%; age 55-64 yrs. = 30%; 65-74 yrs. = 20%; age 75 yrs. or older = 10%. For caregivers, we expect that we'll enroll 38% male caregivers and 62% female caregivers.⁴¹ In the Strong, Highland, FF Thompson, and Rochester General Hospital Renal Group, we have 9 female nephrologists, 19 male nephrologists, and 1-3 fellows/yr. Faculty age ranges from 34-65 plus.
- (c) **Racial and Ethnic Origin:** We do not restrict enrollment based on race or ethnic origin. The demographics of the population in the Greater Rochester area in 2010 was 77% White, 16.2% Black or African American, 8.5% Hispanic or Latino (either Black or White). We expect the racial and ethnic distribution of the enrolled subjects to be the following (Tables 1, 2 & 3): However, to encourage recruitment of minority participants, we will seek input on the study protocol from minority patients. Additionally, a coach will have the option to do home visits in order to prevent financial burden on the participants.

Table 1. Racial and Ethnic Category of Physicians
(Expected number of participants = 10)

Racial/Ethnic Category	
White (including Latinos or Hispanics)	8 (80%)
Asians	2 (20%)

Table 2. Racial and Ethnic Category of Patients
(Total participants = 60)

Racial/Ethnic Category	
White (including Latinos or Hispanics)	46 (77%)
Black or African American (including Latinos or Hispanics) 16%	10 (16%)
Other	4 (7%)

Table 3. Racial and Ethnic Category of Caregivers
(Expected number of participants = 36)

Racial/Ethnic Category	
White (including Latinos or Hispanics)	27 (77%)
Black or African American (including Latinos or Hispanics) 16%)	7 (16%)
Other	2 (7%)

- (d) **Vulnerable Subjects:** We do not plan to include vulnerable subjects such as children, pregnant women, fetuses, or prisoners. Employees (physicians/fellows) will be assured that taking part in research is not a part of their duties, and refusing to participate in the study will not affect their job. To ensure their autonomy, the research coordinator (rather than the PI) will consent them. We realize that some patients in the study may have a cognitive or decisional impairment. To protect the rights of these patients, we have specified all the details in section 4.2 (Process of Consent). Caregivers lacking capacity will be excluded from the study.

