5. METHODS AND STUDY PROCEDURES

5.1. Overview of the Procedures

After a **nephrologist** has consented for the study, he/she will be asked to complete a study entry questionnaire. It should require no more than 15 minutes to complete the questionnaire (**Table 5**).

Randomization: After enrollment and baseline data are obtained, nephrologists will be randomized to either the intervention or control group of the study by study personnel who will be blinded to their identities. This is a cluster RCT. Thus, patients of nephrologists in the intervention group will be assigned to the intervention group; patients of nephrologists in the control group will be assigned to the control group.

After a **patient coach** has completed all coaching sessions and follow up calls with their assigned subjects they will be asked to participate in a qualitative interview.

After a **physician coach** has completed all coaching sessions and follow up correspondence with nephrologists enrolled in the intervention arm they will be asked to participate in a qualitative interview.

At study completion all assisting **research coordinators** will be asked to participate in a qualitative interview.

Intervention:

Nephrologist component: We will conduct a pre-research focus group or individual sessions for nephrologists to learn about the skills and barriers that will help them become better communicators for shared dialysis decision-making. Nephrologists in the intervention group may be provided with supplies such as a notebook, pen and highlighter. They will then participate in a brief value affirmation exercise and goals of communication training at the time of enrollment and completion of their baseline assessments. Nephrologists will receive links to watch 5 communication training videos and then partake in up to three Zoom educational sessions, each approximately 45-60 minutes in duration, approximately 1-3 weeks apart, with standardized patient instructors (SPI) who will be enacting roles of patients with advanced kidney disease. The SPI will provide immediate oral feedback to the nephrologist. The specific communication behaviors that will be targeted include: (1) engagement, by acknowledging and prioritizing patient concerns (2) empathy (3) ASK-TELL-ASK approach (4) decision-making skills:

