(a) value/preference clarification (b) compare options including conservative management (c) choose an option that seems to best fit with patient preferences. An effort will be made to tailor these sessions to the individual needs of a nephrologist by reviewing the identified needs and discussion with the coach. The communication coaching session will be audio-recorded, and nephrologists will receive written feedback via email following the sessions to reinforce their

learning. A manual and fidelity checklist will be developed to deliver this component of the intervention.

Patient recruitment at Strong, Highland and Rochester General Hospital will start once a nephrologist in the intervention group has completed at least two communication coaching sessions. At the end of each patient visit, nephrologists will be asked if (a) a preliminary RRT decision has been made? If not, is there a plan to discuss it in the next visit? Once a patient has made an RRT decision or has seen the nephrologist twice, either in-person or via Zoom, a final set of assessments will be completed. At the end of the study, to check for contamination, nephrologists in the intervention group will be asked if they were able to share newly learned communication skills with the nephrologists in the control group.

Upon completion of the decision-making process with the nephrologist, depending on patient's choice, patients will be given a summary of the 'next steps,' prepared in conjunction with the treating nephrologist. A copy will be given to the patient by the research coordinator in-person or via mail: (1) When does the patient need to finalize the decision (only if the decision has not been made after two visits)? (2) At what GFR level, access will be placed? (3) Symptoms suggestive of need for dialysis (4) when will dialysis need to be initiated?

Patient component (and caregivers, if available):

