7. SUBJECT WITHDRAWALS

Participants will be advised that they have the right to withdraw from the study at any time without prejudice. Participants may also be withdrawn from the research without their consent in the event of acute worsening of their kidney disease needing initiation of hemodialysis before completion of the study. If a caregiver withdraws from the study, another caregiver identified by the patient will be approached. All participants who withdraw from the study will be offered an exit interview.

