
Table 5. Timing of administration of assessments for physicians

	Measurement	References (if applicable)	# of items	Time of completion
Aim-1	Feasibility, acceptability and appropriateness of the intervention measures	Weiner et al, Implement Science, 2017	12	Study completion
	Fidelity of the DIAL-SDM intervention	NA	30	After the completion of each coaching session.
	Qualitative Interviews		7	Study completion
Aim-2	Physician-patient communication: Active Patient Participation Coding (APPC) scores	Street et al, Soc Sci Med. 2007	NA	Study completion (audio scripts)
	Shared decision-making: OPTION scale	Elwyn G, Qual Saf Health Care. 2003	12	Study completion (audio scripts)
	Comfort with shared decision making	Degner et al, J of Clin Epidemiology, 1992	5	Study entry Study completion
	Comfort with medical paternalism	Duberstein et al, JOSM 2019	1	Study entry
Other potential co-variates	Physician demographics and training experience	NA	7	Study entry
	Value Affirmation Exercise		9	Study entry (Intervention group)

Table 6. Timing of administration of assessments for patients

	Assessment	References if applicable	# items	Time of completion
Aim-1	Feasibility (patients approached vs enrolled)	Weiner et al, Implement Science, 2017	Feasibility of the intervention measure	0-3 months (after last coaching session)
			Feasibility of the Question Prompt List	
			Feasibility of the Education Booklet	
			Feasibility of Education video	
	Acceptability	NA	Qualitative interviews	0-3 months (after last coaching session)
		Weiner et al, Implement Science, 2017	Acceptability of the Intervention measure	0-3 months (after last coaching session)
			Acceptability of the Question Prompt List	
			Acceptability of the Education Booklet	
		NA	Fidelity	After the coaching session (audio recordings)
Aim-2	Physician-patient communication: Active Patient Participation Coding (APPC) scores	Street et al, Soc Sci Med. 2007	NA	3-6 months at Study completion (audio scripts)
	Shared decision-making: OPTION scale	Elwyn G, Qual Saf Health Care. 2003	12	3-6 months at Study completion (audio scripts)
	Shared decision-making questionnaire	Kristen L et al. Patient Educ Couns. 2010	9	0-3 months 3-6 months at Study completion

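### Aim 1 feasibility and acceptability ratings are scheduled only at the end, while nephrologists lost during training are replaced, so the ratings come mainly from those who stay

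*Combined protocol and SAP*

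**What the plan says.** **Replacement.** Section 3.1(a): "For physicians who withdraw from the study prior to the enrollment of their own participating patients, they will be replaced with additional physicians". The total is capped at 16.

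**Order of events.** Section 5.1: "After enrollment and baseline data are obtained, nephrologists will be randomized to either the intervention or control group". Intervention nephrologists then do a values exercise, five videos and up to three coaching sessions of roughly 45-60 minutes. Patient recruitment "will start once a nephrologist in the intervention group has completed at least two communication coaching sessions". Control nephrologists have no training during the study.

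**Rating times.** Table 5 lists "Feasibility, acceptability and appropriateness of the intervention measures" for nephrologists once, at study completion. Tables 6 and 7 schedule the patient and caregiver scales at "0-3 months (after last coaching session"). Under Section 5.2, the interviews on feasibility and acceptability follow the last meeting with the nephrologist.

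**Fidelity.** Table 5 times the nephrologist checklist as "After the completion of each coaching session". Table 6 takes patient fidelity from the session recordings.

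**Information on those who do not stay.** Section 4.2 logs physicians, patients and caregivers approached, enrolled and declined, with reasons for refusal. Section 7: "All participants who withdraw from the study will be offered an exit interview". For patients, Section 5.2 limits that interview to the main reason and suggestions. Tables 6 and 7 list it with 3 items, and Table 5 has no such row.

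**Analysis and use.** Section 11.1 calls the Aim 1 analysis mainly descriptive. Section 2.2 makes planning of a larger trial depend on feasibility and acceptability being shown.

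**The concern.** Feasibility and acceptability are the primary aim, and the result decides whether a larger cluster trial is designed. A nephrologist who leaves during training is the plainest evidence that the training is hard to deliver. Under this schedule that person is likely to leave without giving a rating, and someone else takes the place. A patient or caregiver who stops part-way may also miss the single rating point. If leavers think less well of the intervention than stayers, which is the natural expectation, the summary of the ratings is too high and nothing in the planned report would show it.

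The same selection reaches Aim 2. Replaced nephrologists contribute no patients, so the preliminary effect sizes would compare nephrologists who got through training with controls who had none to get through.

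**Working it through.** The plan states no figure for this point (no retention target, dropout rate or success threshold), so there is nothing to reproduce. The check traces who can be rated and when, and then illustrates the size.

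**1. Does loss during training fall inside the replacement window?** Randomisation precedes training, and at least two of up to three sessions precede patient recruitment (Section 5.1). Replacement applies until a physician's own patients enrol (Section 3.1). So a withdrawal during the first two sessions comes after randomisation and leads to replacement. A withdrawal around a third session may fall on either side. The recruitment sentence names three of the four sites and omits FF Thompson.

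**2. Which Aim 1 data exist for a leaver?**

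| Measure | Scheduled time | Available for a leaver? |
|---|---|---|
| Nephrologist scales | Study completion | Not scheduled |
| Patient and caregiver scales | After last coaching session | Only if this means the last session attended |
| Feasibility and acceptability interviews | After last nephrologist meeting | Not scheduled |
| Fidelity | By session | Yes, for sessions held |
| Recruitment log | Up to enrolment | Silent on retention |
| Exit interview | At withdrawal, if accepted | Reasons and suggestions, not the scales; for physicians only a general offer |

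**3. Nephrologist retention.** Retention = slots / (slots + replaced leavers). Assumption: 16 nephrologists split 1:1, giving 8 intervention slots. The documents also mention 12 (Section 9.1) and 10 (Table 1) and give no allocation ratio, so 6 slots are shown too.

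| Replaced leavers | 8 slots | 6 slots |
|---|---|---|
| 0 | 8/8 = 100% | 6/6 = 100% |
| 1 | 8/9 = 89% | 6/7 = 86% |
| 2 | 8/10 = 80% | 6/8 = 75% |
| 3 | 8/11 = 73% | 6/9 = 67% |
| 4 | 8/12 = 67% | 6/10 = 60% |

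A count of filled slots is complete in every row. Exact binomial 95% limits with 2 leavers:
- 8/8: lower limit 0.025^(1/8) = 0.631, so 63-100%.
- 8/10: the 0.025 quantile of Beta(8, 3) is 0.444 and the 0.975 quantile of Beta(9, 2) is 0.975 (0.9748), so 44-97%.

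**4. Patient ratings.** Assumption: 30 of the 60 patients are in the intervention arm, 6 leave unrated, and 22 of the other 24 rate the intervention favourably.
- Among raters: 22/24 = 91.7%.
- No leaver favourable: (22 + 0)/30 = 73.3%.
- Half of the leavers favourable: (22 + 3)/30 = 83.3%.
- All leavers favourable: (22 + 6)/30 = 93.3%.
- For the raters' figure to hold for all 30, 30 × 22/24 = 27.5 would have to be favourable, that is 27.5 − 22 = 5.5 of the 6 leavers.

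**The case against.** The strongest reply is that the plan collects more on non-stayers than the scales suggest, and that replacing a nephrologist does not by itself prevent that person from being counted. Fidelity is recorded by session, the recruitment log covers those approached and declining, and everyone who withdraws is offered an exit interview. This stands in part. It takes fidelity out of the concern, and it shows that feasibility of recruitment is measured independently of retention. It does not close the gap, because the log ends at enrolment and the exit interview as described omits the scales.

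For patients the reply has some force. Section 5.1 expects most to need one coaching visit, so many leavers after coaching could still be rated if the time point means the last session attended. A patient who leaves before any coaching has little to rate. Some are withdrawn for acute worsening of kidney disease (Section 7), which says nothing about acceptability.

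Several stronger readings are tempting but not supported:
- *The whole primary aim is measured only in stayers.* This is wrong for fidelity and too strong for feasibility.
- *Everyone who finds the training infeasible leaves and is replaced.* Some may stay and rate it poorly, or leave after their patients have enrolled.
- *The plan would report 8/8 completing.* It defines no completion proportion. The fault is a missing denominator rule, not a rule that excludes leavers.
- *Replacement is one-sided, or fills the vacated arm.* The rule covers both arms, and nothing says where a replacement goes. Only training-driven loss is confined to the intervention arm.
- *Counting leavers caps acceptability at 73%.* That figure is the floor of the range, and 93% is the ceiling.

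**Conclusion.** The point holds for the feasibility and acceptability ratings. Their single late time point, the replacement of nephrologists lost during training and the absence of a denominator rule together mean that the ratings come mainly from stayers. They are likely, though not certain, to be too favourable for the decision they serve. If nobody withdraws, or if leavers would have rated as stayers do, there is no distortion.

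The size cannot be fixed from the documents. The retention and rating figures rest on assumed counts and an assumed 1:1 split. They show what a few leavers could do in a pilot of this size and do not predict the number of leavers. The plan should be changed before Aim 1 is reported, but the trial's other measurements do not depend on this.

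**What to change.** 1. Offer the short feasibility and acceptability scales at withdrawal to intervention nephrologists, patients and caregivers who have begun the intervention. Add an exit-interview row to Table 5.
2. In Section 11.1, define the Aim 1 denominators as all nephrologists randomised to the intervention, including those later replaced, and all consented intervention patients and caregivers. Report the number rated out of each.
3. Report retention, withdrawals and replacements by arm, with timing relative to training.
4. Give a worst-case lower bound that counts unrated leavers as unfavourable, labelled as a sensitivity figure. Show separately those withdrawn for acute kidney worsening.
5. State that any replacement nephrologist is randomised with allocation concealed.
6. Say whether the patient and caregiver time point means the last session planned or the last attended.

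The cost is protocol and analysis wording plus a few questionnaire items at exit. The reported feasibility figure may also be less favourable.

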9.1. Risks to Human Subjects

(a) Human subject's involvement and characteristics

Study subjects are nephrologists (n=12 or more/less), CKD patients (n=60) and their caregivers (n=36 or more/less). All subjects will provide informed consent. Subjects under age 21 are excluded from the study.

(b) Potential risks

Privacy and confidentiality. There is a small potential for risk to patients and caregivers of disclosure of private material. Research staff will need to have patient and caregiver contact information including telephone number and address available for follow-up. Alternative procedures are not available.

Psychological or physical risk. There is potential risk for minor psychological discomfort among patients and caregivers while completing questionnaires or talking about symptoms of CKD, prognosis, and their other experiences during treatment for the illness. Patients and caregivers will be instructed to inform their physician as well as the research staff if they wish to refrain from discussing aspects of their illness or refuse to answer a particular question. Physical risks in this study – that is, risks associated with voluntarily responding to oral surveys and questions asked by a research assistant are low.

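### The stated 80% power for a 15-point OPTION difference does not follow from its own inputs, which give about 97–99% at 12 nephrologists without covariates

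*Combined protocol and SAP*

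**What the plan says.** The only quantified justification of the sample size is in Section 3.1(a). It starts from "With a total sample size of 60 patients", with "approximately 5 patients per nephrologist depending on the total number of enrolled nephrologists". It then claims that "we would have 80% power at an alpha of 0.05, assuming a coefficient of variation of cluster sizes as high as 0.5", adds an intraclass correlation of 0.1, and gives the target as "to detect mean differences of at least 15 points (standard deviation 11) on the OPTION scale scores".

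Section 11.1 makes all p values two-sided. It specifies regression models that account for patients nested within physicians, and it puts five physician-level covariates into every regression: gender, years of experience, practice style, previous communication training and fellow status.

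The plan gives no formula, allocation ratio, number of clusters per arm, degrees of freedom or allowance for loss for this calculation. The number of nephrologists appears in three places:
- Section 3.1(a): "Nephrologists (n= up to 16", which is a cap.
- Section 9.1: "Study subjects are nephrologists (n=12 or more/less", which agrees with 60 patients at 5 each.
- Table 1 in Section 3.1: "Expected number of participants = 10".

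**The concern.** A 15-point difference with a standard deviation of 11 is 15/11 = 1.36 standard deviations. That is a very large effect, and 60 patients with a modest intraclass correlation should detect it with well over 80% power. Either the power or detectable difference is misstated, or one of the inputs is, or a correction was applied that the plan does not describe. A reader cannot tell which.

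Two things are at stake. The first is interpretation: the paragraph says that only effects of about 1.36 standard deviations are reliably detectable, whereas its inputs put that threshold at roughly 0.9 to 1.0 (9.8/11 = 0.89; 10.9/11 = 0.99). The second is re-use: Sections 2.2 and 3.1(a) look ahead to a larger cluster trial. A misreported standard deviation or intraclass correlation could be carried into its planning if this paragraph were taken as a source.

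**Working it through.** **Inputs.** From Section 3.1(a): N = 60; mean cluster size m = 5, so k = 60/5 = 12 nephrologists; CV of cluster sizes 0.5; ICC 0.1; SD 11; difference 15; alpha 0.05. From Section 11.1: two-sided tests. Assumed: 1:1 allocation, and SD 11 read as the total SD.

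**Trying to reproduce the 80%, at k = 12.**

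1. Design effect for unequal clusters: DE = 1 + ((1 + CV²)·m − 1)·ICC = 1 + (1.25 × 5 − 1) × 0.1 = 1.525.
2. Effective sample size: 60/1.525 = 39.3, or 19.67 per arm.
3. Standard error of the difference: 11 × √(2/19.67) = 3.51.
4. Non-centrality: 15/3.51 = 4.28.
5. Power, normal approximation: Φ(4.28 − 1.96) = 99.0%. Power, non-central t with k − 2 = 10 degrees of freedom (critical value 2.228): 97.0%.
6. Difference detectable with 80% power: (1.96 + 0.842) × 3.51 = 9.8 points (normal); 10.9 points (t).

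The stated 80% is not reproduced.

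**Across the nephrologist counts in the plan (60 patients, no covariates).**

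| k | m | DE | SE | Power at 15, normal | Power at 15, t (k − 2 df) | 80%-power difference, normal / t |
|---|---|---|---|---|---|---|
| 10 | 6 | 1.65 | 3.65 | 98.4% | 94.8% | 10.2 / 11.7 |
| 12 | 5 | 1.525 | 3.51 | 99.0% | 97.0% | 9.8 / 10.9 |
| 16 | 3.75 | 1.369 | 3.32 | 99.5% | 98.7% | 9.3 / 10.0 |

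**Other readings, at k = 12 (normal / t).**
- SD 11 taken as the within-cluster SD (total SD 11/√0.9 = 11.6): 98.2% / 95.4%.
- 48 of the 60 patients analysed: 97.9% / 94.8%.
- 30 of the 60 analysed: 92.4% / 86.3%.

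**What would give 80% at 15 points with k = 12.** An SD of about 16.8 (normal) or 15.1 (t), or an ICC of about 0.49 (normal) or 0.36 (t). Section 3.1(a) states none of these.

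**Charging the five physician covariates to the between-cluster degrees of freedom (k − 7), with no gain in precision.**

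| k | df | Power at 15 | 80%-power difference |
|---|---|---|---|
| 10 | 3 | 77.5% | 15.5 |
| 12 | 5 | 92.2% | 12.3 |
| 16 | 9 | 97.9% | 10.5 |

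**The case against.** The strongest reply is that the analysis planned in Section 11.1 is not the unadjusted comparison computed above. With so few clusters, five physician covariates are costly. At 10 nephrologists the adjusted calculation gives 77.5%, close to the stated figure. At 11 it gives 87.4%, or about 79% if practice style takes two degrees of freedom (an assumption; the plan does not say how it is coded). This reply stands to the extent that the plan gives no formula or degrees of freedom, so no single figure can be called the true detectable difference. It does not rescue the statement. Section 3.1(a) mentions no covariate adjustment, and its 5 patients per nephrologist imply 12 clusters, where the same adjustment still gives 92.2%.

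It can also be said that little depends on the figure. The primary aim is feasibility, acceptability and fidelity, analysed mainly descriptively. OPTION is one of several Aim 2 outcomes. Section 2.2 makes the larger trial depend on feasibility and acceptability, and Section 3.1(a) says effect sizes will come from the pilot data. All of this stands, and it limits the severity of the point.

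Three stronger readings are tempting, and the documents support none of them:
- *The trial is wrongly sized or underpowered.* The error runs the other way: on the stated inputs, 60 patients give more power for 15 points than claimed.
- *Enrolment could be cut.* That depends on how many nephrologists remain. At 5 patients each, 30 patients in 6 clusters give 85.6% by the normal approximation but only 62.6% by t with 4 degrees of freedom.
- *The plan gives three contradictory cluster counts.* A cap of 16 is compatible with roughly 12. Only Table 1's expected 10 conflicts with the 12 implied by the calculation.

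**Conclusion.** The point holds as a reporting error. At 12 nephrologists with 5 patients each, 1:1 allocation, a two-sided test and no covariates, the inputs give about 97% (t) to 99% (normal) power for 15 points. That is 17 to 19 percentage points above the stated 80%. The difference detectable with 80% power is about 10.9 (t) or 9.8 (normal) points, not 15. Over 10 to 16 nephrologists the ranges are about 95–99.5% and 9.3–11.7 points.

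These figures are conditional on the unadjusted model. With the physician covariates charged to the degrees of freedom and no precision gained, power runs from about 78% at 10 clusters, through 92% at 12, to 98% at 16. The plan does not say that this was the basis.

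The error is conservative and affects neither enrolment nor the primary aim. It should be fixed, but the conduct of the trial does not depend on it.

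**What to change.** Restate the power sentence in Section 3.1(a), for example: 60 patients in about 12 nephrologists (1:1 allocation, ICC 0.1, cluster-size CV 0.5, SD 11, two-sided alpha 0.05, t with 10 degrees of freedom, no covariates) give 80% power for an OPTION difference of about 11 points, and about 97% for 15 points.

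If the 80% at 15 points came from a different SD, ICC, difference, number of clusters or degrees of freedom, correct that input instead and name the formula. If the calculation was meant for the covariate-adjusted model, say so and give the degrees of freedom.

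Align Table 1's expected 10 nephrologists with the number used in the calculation. The cap of 16 can stay.

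The cost is one paragraph of protocol wording and one table entry. Enrolment, procedures and analyses do not change.
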